RESEARCH PROTOCOL

Date	5-15-19
Title	Utilization of the mirror during pelvic exams: Does it reduce patient vulnerability and discomfort?
Principal Investigator	[name]
Sub-Investigators	[name]; [name]; [name]; [name] MSc; [name], DO; [name]
Research Specialist	[name], MS
Department	Department of OB/Gyn, Division of Urogynecology and Reconstructive Pelvic Surgery
Hatton #	18-107

IRB Review Type: Exempt Expedited Full Board

Purpose of Study

Primary Aim:

- To determine if using a mirror during the patient's pelvic examination (MPE) decreases patients' degree of vulnerability and discomfort.

Secondary Aims:

- To assess patient degree of anxiety, sense of control, and embarrassment during pelvic exam with and without the mirror.
- To assess patient awareness of personal pelvic anatomy and diagnosis following pelvic exam with and without the mirror.
- To assess patient willingness to have mirror during each subsequent pelvic exam
- To assess patient satisfaction with their exam, with and without mirror.
- To describe any differences between patients that agree to use of the mirror for their exam compared to those who refuse the mirror.
- To determine if implementing the MPE increases average length of time of pelvic examination.

Hypothesis or Research Question

- We hypothesize that the MPE will decrease the level of vulnerability and discomfort experienced during the pelvic examination.

Background

In Obstetrics and Gynecology and its gynecologic subspecialties, the pelvic examination is routine practice for screening and diagnostic purposes. Nevertheless, due to their intimate nature, pelvic examinations may result in loss of control, embarrassment, discomfort and anxiety [1-3]. Patients that present for urogynecologic care are a unique subset of women due to their advanced age, and nature of their disorder. As such, these patients may be more likely to express anxiety and concern about their visit [3].

With the trend of hospital improvement and quality, patient centered care and experience are now a main topic of improvement. The environment in the outpatient setting is different from that of an inpatient setting however; the patient's experience is just as complex. Patients who feel emotionally comfortable are more likely to feel a greater sense of empowerment, enablement and engagement [4]. This is intertwined with patient participation and ultimately affects the patient experience [5].

The mirror pelvic exam (MPE) has been a proposed technique to decrease patient anxiety and improve comfort during an already uncomfortable examination. However, little research has focused on this modality to date. An early report from the 1970's described 90% of the patients felt more relaxed by utilization of the mirror and 76% revealed they would like a gynecologic problem demonstrated with a mirror [6]. A small study performed at California Polytechnic State University studied 15 females who underwent an MPE. Results were favorable revealing that 67% of the patients aged 18-26 years were more relaxed and had less discomfort whilst using the MPE. Additionally, it was found that 100% of the patients would like to have the mirror used in the future if they were to experience a gynecological problem and 92% would recommend this to a friend [7].

To date, there have been no trials regarding the utility of the MPE in a population with prolapse, incontinence or pelvic floor disorders. By studying this tool, we could understand better the utility of the MPE and discover if there is a specific patient population or situation in which this tool should be offered to ease patients' sense of vulnerability, pain, and anxiety.

Research Plan

- **Study Design**
Prospective Two-cohort Study
- **Setting for the study**
 - All new patients to Cincinnati Urogynecology Associates, TriHealth presenting to one of four outpatient clinics (Clifton, West Chester, Kenwood, Anderson) will be eligible.
 - They will then be approached by either a research coordinator, attending physician or fellow in the exam room or in the research coordinator's office prior to the start of their visit and offered enrollment.
 - If they agree to participate they will answer a brief questionnaire about demographics, personal experience with pelvic exam, the purpose of their visit and whether they would agree to have a mirror utilized during their pelvic exam that day.
 - If they agree to have a mirror used, then they will undergo the examination with the use of a mirror during the physician examination of the pelvic area, and receive information about the anatomy being shown. No other changes will be made to the exam performed.
 - If they decline a mirror then they will undergo our standard pelvic examination.
 - All enrolled patients will then be given a questionnaire at the completion of their pelvic exam.

- **Participants**
 - Study population: All women 18 years of age to 80, who undergo pelvic exam by a physician at Cincinnati Urogynecology Associates, TriHealth will be approached for recruitment.
 - Inclusion/Exclusion criteria:
 - Inclusion
 - Adults 18 years of age to 80
 - New patients undergoing a pelvic exam performed by a physician at Cincinnati Urogynecology Associates, TriHealth
 - Exclusion
 - Existing patients
 - Unwillingness to participate in the study
 - Physical or mental impairment that would affect the subject's ability to visualize the mirror during examination or to complete questionnaires
 - Inability to understand English
 - **Sample size**
 - A sample size was calculated to be 68 patients in each arm based on the following:
 - A prior study by Seehusen D. et al, evaluated the vulnerability and discomfort level in patients who underwent a pelvic exam using stirrups or no stirrups. Because there are no prior studies that have evaluated vulnerability or discomfort using the mirror during pelvic examination, this study was used to develop a sample size [8].
 - The difference in mean VAS on level of vulnerability for two groups was selected to be 10.5 mm with SDs for 16.3 and 25.8 with/without intervention, respectively.[8]
 - Two group Satterthwaite t-test with a 0.05 two-sided significance level was used for sample size calculation.
 - The power was set at 80 %.
 - Assuming an estimated drop-out rate of 15%, the number of patient enrollment per arm was set to 80, for a total of 160 patients.
- **Data Collection**
 - Primary Outcome:

- Patient's level of vulnerability and discomfort before and after the pelvic exam.
- Secondary Outcomes:
 - Patient's sense of loss of control, anxiety and embarrassment during the pelvic exam.
 - Patient's level of understanding of pelvic anatomy and diagnosis after the pelvic exam.
 - Changes in the time of the examination as calculated by time performing the pelvic exam (will be performed using a timer in the room).
 - Differences in demographics and medical history between those that decline the MPE and those that consent to the MPE.
 - Patients' overall satisfaction of the entire visit.
 - Likelihood of physician referral to friends or family.
 - Patients willingness to have the MPE during future visits.
- General demographic data and medical data
 - DOB, age, race, weight, height, BMI, religion, education level, past medical history, date of exam, duration of exam, chief complaint on initial visit, sexual activity level, outcome of visit (ie. Surgical intervention, medical intervention, none).
- **Intervention or experimental aspect of the study**
 - The patients will be addressed on their first visit in the exam room or in the research coordinator's office prior to the start of their visit. Each will be given a description of the study by a research coordinator, attending or fellow.
 - Once consent and enrolled, whether or not they refuse to have the mirror pelvic exam or not, they will be given a pre-examination questionnaire.
 - Of the patients who agree to have the mirror pelvic exam, they will then undergo routine pelvic examination by a physician with the usage of a mirror in the room. This mirror will be a roll-in mirror that is positioned in such a manner that provides the patient with adequate visualization of her female parts.
 - All physicians will be instructed on the terminology and descriptions to utilize with the exam to standardize the experience with the mirror.
 - The pelvic examination will be timed from the start of palpation of the external female genitalia and stopped at the time of last genital contact.
 - At the end of the visit, the patient will be given a questionnaire that characterizes her experience.
- **Statistical Analysis**
 - Descriptive statistics will be generated for demographic information such as age, race, BMI, Parity. Continuous variables such as level of vulnerability, pain, and anxiety on VAS will be analyzed using independent samples t-tests or Mann-Whitney U test for significant difference between groups. A multiple linear regression will be utilized for adjusting confounding variables. Categorical variables will be tested using the Fisher's exact or Pearson Chi-square tests.

Ethical Considerations

- **Informed consent**
 - Patients who agree to participate in the study will sign a written informed consent. They will be consented by one of the stated investigators or trained Research Nurse and they will receive a copy of the signed informed consent statements (ICS). A copy will be put in their medical file.
- **Privacy information**
 - Extensive efforts will be made to ensure and maintain participant confidentiality. All identifying information will be maintained in a secure area at all times. Source documentation will be maintained in a separate folder. When documentation has to be made available for data analysis, copies of the source (Excel spreadsheets) with only Subject ID number visible and personal information obscured will be used. All communication between staff members regarding participant data will occur via the Subject ID number only. However, identifying information will be retained in the original/source documents.
 - The participant will be logged in the Excel spreadsheet and assigned a Subject ID number. Each participant will be assigned the next available Subject ID number. Once each Subject ID number has been assigned, it will not be reassigned. The Excel spreadsheet will be stored on a password protected, encrypted TriHealth computer for ten years following study closure, and then purged.

Estimated Period of Time to Complete Study	
When will study begin?	December 15 th , 2018
Protocol Development Completed	November 5 th , 2018
Admin Review Time	2 weeks
IRB Approval	December 18,2018
Data collection	Subjects to be enrolled starting January 1, 2019
Data analysis	January 2020

- **When and how will results be disseminated?**
 - Submit for abstract presentation at national/international meeting and publication

References

[1] Larsen, M. "Not so Bad after All..., Womens Experiences of Pelvic Examinations." *Family Practice*, vol. 14, no. 2, Jan. 1997, pp. 148–152., doi:10.1093/fampra/14.2.148.

[2] Haar, Esther, et al. "Patients' Attitudes toward Gynecologic Examination and to Gynecologists." *Medical Care*, vol. 15, no. 9, 1977, pp. 787–795., doi:10.1097/00005650-197709000-00006.

[3] Bates, Carol K., et al. "The Challenging Pelvic Examination." *Journal of General Internal Medicine*, vol. 26, no. 6, Dec. 2011, pp. 651–657., doi:10.1007/s11606-010-1610-8.

[4] Williams, Anne M, et al. "Further Psychometric Testing of an Instrument to Measure Emotional Care in Hospital." *Journal of Clinical Nursing*, vol. 20, no. 23-24, Jan. 2011, pp. 3472–3482., doi:10.1111/j.1365-2702.2011.03846.x.

[5] Williams, A M, et al. "Patient Evaluation of Emotional Comfort Experienced (PEECE): Developing and Testing a Measurement Instrument." *BMJ Open*, vol. 7, no. 1, 2017, doi:10.1136/bmjopen-2016-012999.

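### The primary outcome is worded as the level before and after the exam, the hypothesis concerns the level during it, and the plan does not say which rating or contrast is tested

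*Combined protocol and SAP*

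**What the plan says.** The protocol gives the time frame of vulnerability and discomfort in different ways.

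- **Hypothesis or Research Question:** "We hypothesize that the MPE will decrease the level of vulnerability and discomfort experienced during the pelvic examination".
- **Data Collection, primary outcome:** "Patient's level of vulnerability and discomfort before and after the pelvic exam".
- **Data Collection, first secondary outcome:** "Patient's sense of loss of control, anxiety and embarrassment during the pelvic exam". The item after it, understanding of anatomy and diagnosis, is placed after the exam.
- **Purpose of Study, primary aim:** "To determine if using a mirror during the patient's pelvic examination (MPE) decreases patients' degree of vulnerability and discomfort". Here the word *during* describes when the mirror is used; no period is given for the feelings.

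Ratings can come from two forms. Before the exam, under the intervention heading, women are told that "they will be given a pre-examination questionnaire". For the second form, the setting section says "All enrolled patients will then be given a questionnaire at the completion of their pelvic exam", while the intervention section says "At the end of the visit, the patient will be given a questionnaire that characterizes her experience". No rating taken while the exam is in progress is described for any outcome.

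The sample size section uses one between-group difference in mean VAS vulnerability, "selected to be 10.5 mm with SDs for 16.3 and 25.8 with/without intervention, respectively". The Statistical Analysis section compares VAS levels between groups by t-test or Mann-Whitney U test and plans a multiple linear regression for confounders. Neither section names a time point or a change score.

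**The concern.** Read literally, the primary outcome is not the quantity in the hypothesis. The outcome list uses *during*, *after*, and *before and after* as if they were separate periods, and the primary outcome is the one that departs from the hypothesis.

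The difference matters because the mirror is in use only during the physician's examination. A rating made beforehand precedes it. A rating of how the woman feels afterwards can reflect the mirror only to the extent that its effect lasts. A recalled rating of the exam addresses the hypothesis directly.

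The choice between level and change also matters. Women choose their own cohort, so the cohorts may differ before the exam. A comparison of post-exam levels and a comparison of changes then need not agree. With the time point and contrast unspecified, the primary analysis could be settled after the data are seen.

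**Working it through.** **1. The plan's own figure.** Inputs, all from the sample size section: difference 10.5 mm, SDs 16.3 and 25.8, two-sided 0.05, Satterthwaite t-test, 80% power, 15% drop-out.

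- Standard error at 68 per arm: √[(16.3² + 25.8²)/68] = √(931.33/68) = 3.70 mm.
- Satterthwaite degrees of freedom with equal arms: 67 × (265.69 + 665.64)² / (265.69² + 665.64²) = 113.
- Noncentrality: 10.5/3.70 = 2.84. Power from the noncentral t distribution is 80.3% at 68 per arm and 79.7% at 67.
- Enrolment: 68/0.85 = 80 per arm, 160 in total.

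The stated 68 and 80 are reproduced exactly.

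**2. Which contrast does 68 per arm fit?** It is a calculation for one rating compared between two groups. If *before and after* means a change score, each SD is multiplied by √[2(1 − ρ)], where ρ is the correlation between the two ratings. The documents give no ρ. Assuming equal SDs at both times and the same 10.5 mm difference:

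| ρ (assumed) | SD multiplier | n per arm for 80% power |
|---|---|---|
| 0.3 | 1.18 | 94 |
| 0.5 | 1.00 | 68 |
| 0.7 | 0.77 | 41 |

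So 68 is the size for a single-time comparison, and for a change score only if ρ happens to be 0.5. This suggests a single rating was intended, but the plan does not say so, nor which rating.

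**3. Illustration if the rating is the state after the exam.** Suppose a share of the 10.5 mm persists, with the same SDs and 68 per arm. The share is an assumption with no anchor in the documents.

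| Share persisting (assumed) | Difference, mm | Difference / 3.70 | Power |
|---|---|---|---|
| 1 | 10.5 | 2.84 | 80% |
| 0.75 | 7.9 | 2.13 | 56% |
| 0.5 | 5.25 | 1.42 | 29% |
| 0.25 | 2.6 | 0.71 | 11% |

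This shows how sensitive the design would be to such a dilution. It is not an estimate that any dilution occurs.

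**The case against.** The best defence is that *before and after* describes when the two forms are completed. The protocol has exactly those two collection points. The secondary outcomes worded as *during* must also be collected afterwards by recall, so the contrast in wording may be loose drafting. The second form is said to characterize the woman's experience, which could well mean that it asks about the exam. This stands: omission of the exam period cannot be shown without the questionnaire items. It does not remove the mismatch in the outcome line, or the silence of the analysis and sample size sections on the time point.

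A reader might infer more than the documents support:

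- *That the primary measure leaves out the exam altogether, so the study does not test its hypothesis.* This would require knowing that the post-exam item asks for the current state. The items are not available.
- *That the aim, like the hypothesis, specifies the exam period.* In the aim, that wording belongs to mirror use. Only the hypothesis specifies the period.
- *That the outcome is biased towards no difference because feelings ease once the exam ends.* Rapid easing is plausible but not documented, and a fall common to both cohorts cancels in a between-group comparison.
- *That 10.5 mm is an effect on feelings during an exam and does not apply to a later rating.* It comes from the cited stirrups study, and the protocol does not say when or how that study took its ratings.

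**Conclusion.** The concern holds as an inconsistency and a gap in definition. The primary outcome as worded does not match the hypothesis or the secondary outcomes that refer to the exam itself, and at least three primary contrasts remain open: recalled rating of the exam, state afterwards, and change from before.

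The consequence is conditional. If the post-exam item asks for the current state, the primary comparison sees only what persists; if it asks about the exam, the outcome line misdescribes the measure. Either way the text needs correcting. The loss of power in the first case cannot be quantified from the documents, since it depends wholly on the assumed persisting share. The sample size arithmetic is not in question. The amendment is worth making, ideally before any outcome data are compared.

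**What to change.** - Define the primary outcome as vulnerability, and discomfort, experienced during the pelvic exam, each rated on a VAS after the exam.
- Word the post-exam question stem to ask how the woman felt during her exam.
- State in the Statistical Analysis section that this rating is compared between cohorts, with the pre-exam rating as a baseline covariate in the multiple linear regression already planned, not as half of the outcome. The setting section's summary of the pre-exam questionnaire does not mention a VAS rating, so confirm that the form contains one.
- Reconcile completion of the exam with end of the visit as the time for the second form, because this sets the length of recall.

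The cost is a few lines of protocol text and one question stem, plus a baseline item if it is missing. No extra visit or patient is needed, and the 68 per arm stays as it is. The small downside is that the rating becomes a short recall.

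### Women choose whether to have the mirror, but no pre-exam rating of anxiety, sense of control or embarrassment is specified, so a during-exam difference cannot be separated from one already present

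*Combined protocol and SAP*

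**What the plan says.** The Research Plan describes a "Prospective Two-cohort Study". Under Setting for the study, the woman's own decision determines her cohort: "If they agree to have a mirror used, then they will undergo the examination with the use of a mirror"; "If they decline a mirror then they will undergo our standard pelvic examination".

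Data Collection defines the primary outcome at two times: "Patient's level of vulnerability and discomfort before and after the pelvic exam". The emotional secondary outcomes have one time: "Patient's sense of loss of control, anxiety and embarrassment during the pelvic exam". The matching secondary aim under Purpose of Study has the same timing: "To assess patient degree of anxiety, sense of control, and embarrassment during pelvic exam with and without the mirror".

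Every enrolled woman receives a pre-exam questionnaire, whichever cohort she enters (Intervention or experimental aspect of the study). Its content is outlined under Setting for the study: "they will answer a brief questionnaire about demographics, personal experience with pelvic exam, the purpose of their visit", plus whether she would accept the mirror. The list of demographic and medical data contains no emotional rating.

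Statistical Analysis compares the VAS scores, with anxiety named among them, by t-test or Mann-Whitney U. It adds a multiple linear regression to adjust for confounders, without naming any.

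**The concern.** When women sort themselves into cohorts, what they feel beforehand can influence both the choice and the later rating. Anxiety and embarrassment are obvious candidates. The Background raises the first itself, saying of urogynecology patients that "these patients may be more likely to express anxiety and concern about their visit". A woman who arrives anxious will tend to rate the exam as more anxious whether or not a mirror is present. If acceptors and decliners differ on arrival, part of that difference will reappear in the during-exam ratings and look like an effect of the mirror.

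The direct remedy is to measure the same state before the exam and adjust for it. The plan has a before-exam value for vulnerability and discomfort but specifies none for these three outcomes. At stake is the secondary aim on anxiety, control and embarrassment. The primary comparison is affected to a lesser degree, because pre-exam anxiety is also a plausible confounder there. The aim of describing how acceptors differ from decliners would also lack what may be the most informative characteristic.

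**Working it through.** **1. The plan's own figure.** Inputs from Sample size: difference 10.5 mm, SDs 16.3 and 25.8 mm, two-sided 0.05, power 80%, Satterthwaite t-test. With the noncentral t distribution, power is 0.797 at 67 per arm and 0.803 at 68, so 68 is reproduced. For 15% drop-out, 68 / 0.85 = 80 per arm, also reproduced. The sample size arithmetic is not in question.

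**2. What is specified before the exam.**

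| Outcome | Before exam | During or after exam |
|---|---|---|
| Vulnerability, discomfort | specified | specified |
| Anxiety, sense of control, embarrassment | not specified | specified |

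**3. Illustration of the possible size.** The documents give neither the pre-exam gap between acceptors and decliners nor how far it carries into the during-exam rating. Everything in this step is assumption: the vulnerability SDs stand in for all three outcomes, all three are taken as VAS scores in mm, 68 women per arm are analysed, the mirror has no true effect, and the test is unadjusted.

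- Standard error of the difference: sqrt((16.3² + 25.8²) / 68) = sqrt(931.33 / 68) = 3.70 mm.
- Spurious difference: b = pre-exam gap × carry-over.
- Chance of a significant result: Φ(b/3.70 − 1.96) + Φ(−b/3.70 − 1.96).

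| Assumed gap (mm) | Carry-over | b (mm) | b / 3.70 | Chance of p < 0.05 |
|---|---|---|---|---|
| 5 | 0.4 | 2 | 0.54 | 8% |
| 5 | 0.6 | 3 | 0.81 | 13% |
| 10 | 0.4 | 4 | 1.08 | 19% |
| 10 | 0.6 | 6 | 1.62 | 37% |
| 15 | 0.6 | 9 | 2.43 | 68% |

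The nominal figure is 5%. The top row and bottom row are the corners of the assumed range; a 15 mm gap is about 0.7 of the average SD (15 / 21.6) and exceeds the plan's own 10.5 mm difference.

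**4. Sensitivity to the assumptions.** With a gap of 0.2 to 0.5 SD (4.3 to 10.8 mm) and carry-over of 0.3 to 0.7, the noncentral t calculation gives spurious differences of 1.3 to 7.6 mm and rejection in about 6% to 53% of studies. The middle case (0.3 SD, carry-over 0.5) gives 3.2 mm and 14%.

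**5. The opposite direction.** The same sums apply if the more anxious women choose the mirror. Suppose a true benefit of 10.5 mm (borrowed from the vulnerability calculation) and an opposing bias of 6 mm. The apparent benefit is 4.5 mm, 4.5 / 3.70 = 1.22, and the chance of detecting it is about 23% instead of 80%.

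**The case against.** Four objections have force.

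*The ratings may exist.* The questionnaires are not included, and the outline of the pre-exam form is visibly incomplete: it also omits the pre-exam vulnerability and discomfort scores that the primary outcome needs. The item on past experience of pelvic exams might touch on anxiety or embarrassment. A reader might infer that no baseline is taken; the documents do not show that. What stands is that none is specified, and the before-and-after definition of one outcome next to the during-only definition of the other supports this reading.

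*Adjustment is planned.* A reader might infer that nothing in the plan addresses confounding. That is too strong. The regression is not limited to demographics, and pre-exam vulnerability and discomfort could enter it, as could past exam experience, chief complaint and medical history. But no covariate is named, these are at best partial proxies, and a baseline that was never collected cannot be adjusted for. The rejection rates above apply to the unadjusted test and give the regression no credit.

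*The direction is unknown.* It is tempting to say that anxious women decline and that the mirror is therefore flattered. The Background remark concerns urogynecology patients as a group, not acceptors against decliners, and the protocol presents the mirror as a way to reduce anxiety, which could attract anxious women. That feelings influence the choice at all is plausible but not documented.

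*These are secondary outcomes, and the root problem is self-selection.* Both are true. The sole stated hypothesis concerns vulnerability and discomfort. This point is one instance of the wider problem and should not be counted twice if that problem is raised separately; it is set out here because it has its own cheap partial remedy.

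**Conclusion.** The point holds in this form: cohorts are self-selected, no pre-exam rating of anxiety, sense of control or embarrassment is specified, and no covariates are named. Followed as written, the plan cannot tell a during-exam difference in these outcomes from one present before the exam. The bias may run either way.

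Its size cannot be derived from the documents. The 8% to 68% range rests wholly on assumed gaps and carry-over, borrowed vulnerability SDs and an unadjusted test. It shows that moderate imbalances could matter; a reader should not take 68%, or any other row, as an estimate for this study. The weight is moderate: a stated secondary aim is affected, the primary comparison less so, and the remedy is inexpensive.

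**What to change.** - Add VAS items for anxiety, sense of control and embarrassment, as felt at that moment, to the pre-exam questionnaire every woman already receives. Have them answered before her mirror choice is recorded. If the form already holds such items, name them in the protocol.
- Prespecify each pre-exam rating as the covariate for its own during-exam rating, and pre-exam anxiety as a covariate in the vulnerability and discomfort regression.
- Report the adjusted results as associations. The remedy is partial: other reasons for choosing the mirror stay unmeasured, and women hear the study described before they complete the form, so even these ratings may follow knowledge of the mirror.

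The cost is about one minute per woman and a minor amendment. The protocol is dated 5-15-19 and enrolment was planned from January 1, 2019, so women already enrolled may lack the ratings; their comparison on these outcomes should be reported as descriptive only. A side benefit is precision: a pre-exam score correlated r with the during-exam score cuts residual variance by r², for example 36% at an assumed r of 0.6 (0.6² = 0.36).

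### Anatomy understanding has no listed pre-exam measurement, so prior differences between self-chosen cohorts may inflate or mask an apparent mirror effect

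*Combined protocol and SAP*

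**What the plan says.** - **Outcome.** Data Collection, Secondary Outcomes, lists the patient's "level of understanding of pelvic anatomy and diagnosis after the pelvic exam". The matching item under Purpose of Study, Secondary Aims, is "To assess patient awareness of personal pelvic anatomy and diagnosis following pelvic exam with and without the mirror". Both place the measurement after the exam only.
- **Contrast with the primary outcome.** The same Data Collection section defines the primary outcome as "Patient's level of vulnerability and discomfort before and after the pelvic exam".
- **How cohorts form.** Study Design calls this a "Prospective Two-cohort Study". Under Setting for the study, each woman is asked "whether they would agree to have a mirror utilized during their pelvic exam that day". Then: "If they agree to have a mirror used, then they will undergo the examination with the use of a mirror", and "If they decline a mirror then they will undergo our standard pelvic examination". The mirror cohort is also told about the anatomy it is shown.
- **Pre-exam form.** The section on the intervention gives a pre-exam questionnaire to all enrolled women, whatever they decide about the mirror. Setting for the study summarises its content as demographics, past experience of pelvic exams, reason for the visit and the mirror decision. Understanding of anatomy is not mentioned.
- **Analysis.** Statistical Analysis plans a t-test or Mann-Whitney test for continuous variables and a Fisher or chi-square test for categorical ones. It adds a multiple linear regression for confounders, without naming the covariates or the outcomes covered. Education level is among the data collected. No scale or scoring is given for understanding.

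**The concern.** Under randomisation, a post-exam comparison would be adequate, because prior understanding would differ between groups only by chance. Here each woman chooses her cohort, and familiarity with or curiosity about her own anatomy is a plausible reason for the choice. Women who accept may start better informed, or they may be those who know less and want to learn. The documents do not say which.

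Without a pre-exam value, the comparison mixes what women learned at the visit with what they knew on arrival. If acceptors know more beforehand, the mirror may look useful when it is not. If they know less, a real benefit may be hidden. The protocol itself aims to describe how acceptors and decliners differ, so it already treats a difference as possible, but it lists no measurement of the characteristic most relevant to this outcome.

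**Working it through.** **1. The plan's own figure.** The only sample size concerns the vulnerability VAS: difference 10.5 mm, SDs 16.3 and 25.8, Satterthwaite t-test, two-sided 0.05, 80% power.

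- Standard error at 68 per arm = √[(16.3² + 25.8²)/68] = √(931.33/68) = 3.70 mm.
- Noncentrality = 10.5/3.70 = 2.84, on about 113 degrees of freedom.
- Power is 80.3% at 68 per arm and 79.7% at 67, so 68 reproduces.
- With 15% drop-out, 68/0.85 = 80 per arm, or 160 in total, which also reproduces.

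These figures are sound, but they say nothing about the understanding outcome. Only the 68 per cohort is carried forward, as a convenient size. Cohort sizes will in fact depend on how many women accept.

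**2. What a prior gap does to a post-only comparison.** Let *b* be the difference between cohorts in prior understanding, in SD units, and *ρ* the pre/post correlation. Assume a continuous rating with the same SD before and after, a linear relation, and no mirror effect. Then:

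- spurious post-exam difference = *ρ* × *b*
- noncentrality = *ρb* × √(68/2) = 5.83 × *ρb*, on 2 × 68 − 2 = 134 degrees of freedom
- false-positive rate = probability that the noncentral *t* falls outside the two-sided 5% limits

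Neither *b* nor *ρ* is in the documents, so both are assumptions and a range is shown.

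| Prior gap *b* | *ρ* = 0.3 | *ρ* = 0.5 | *ρ* = 0.7 |
|---|---|---|---|
| 0.2 SD | 0.06 SD → 6.4% | 0.10 SD → 8.9% | 0.14 SD → 12.8% |
| 0.3 SD | 0.09 SD → 8.2% | 0.15 SD → 14.0% | 0.21 SD → 22.9% |
| 0.5 SD | 0.15 SD → 14.0% | 0.25 SD → 30.4% | 0.35 SD → 52.6% |

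Each cell gives the spurious difference and the resulting chance of a significant result when the nominal level is 5%. The sign of *b* is unknown. If it is negative, the same shift works against a true benefit.

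**3. What a pre-exam rating would do.** With the same item as covariate, the adjusted difference is the post-exam difference minus *ρ* times the pre-exam difference: *ρb* − *ρb* = 0 under these assumptions. Measurement error in the rating, and confounders it does not capture, would leave part of the bias in place.

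**The case against.** **The form may already contain the item.** Neither questionnaire is reproduced, and the summary of the pre-exam form is evidently incomplete: vulnerability and discomfort are to be measured before the exam, yet neither is in the list. A reader might infer that the form has no understanding item. The documents do not support that. They show only that the protocol text does not provide for one. This objection stands, and the fix allows for it.

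**The regression may deal with it.** Confounder adjustment is planned, and education, medical history and earlier pelvic exam experience are available. So it would be too strong to say that prior knowledge will be read as a mirror effect. But the covariates are unnamed and these variables are only proxies; no model can adjust for prior understanding that is not recorded. If the item is categorical, the stated tests carry no adjustment and a linear model would not suit it.

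**The size is assumed.** This is correct. The gap, the correlation, the continuous scale, the unadjusted t-test and the equal cohorts are all assumptions, and the mild cases are near the nominal 5%. The rates are not expected values.

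**The remedy is partial.** This is also correct. A self-rating captures perceived knowledge and does not measure the wish to learn. Only the mirror cohort is stated to receive the anatomy explanation, so prompting by a pre-exam question might act differently in the two cohorts.

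**The weight is small.** The sole hypothesis concerns vulnerability and discomfort, and this point touches half of one secondary outcome. That limits its priority but does not remove the gap.

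**Conclusion.** The point holds in a limited form. Anatomy understanding is defined only after the exam, is compared between cohorts formed by the women's own choice, and has no listed pre-exam counterpart. As written, the plan cannot adjust directly for prior understanding, so an apparent mirror effect on this outcome may be inflated or masked.

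The size cannot be derived from the documents. Under the stated assumptions (prior gap 0.2 to 0.5 SD, correlation 0.3 to 0.7, 68 per cohort, unadjusted t-test, no true effect), the false-positive rate runs from 6.4% to 52.6%. A reader might conclude that the plan favours the mirror. The documents give no basis for a direction.

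This is a worthwhile optional improvement. It is neither a contradiction nor a calculation error, and it does not affect the primary outcome or the sample size.

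**What to change.** 1. Put the same self-rated anatomy-understanding item on the existing pre-exam questionnaire. If it is already there, state this in the protocol.
2. State the scale, and name the pre-exam rating and education level as covariates for the post-exam rating. Use linear regression if the rating is continuous, and an ordinal or logistic model if it is categorical.
3. Leave the diagnosis item post-exam only, since these are new patients.
4. The protocol is dated 5-15-19 and enrolment was planned from January 1, 2019, so some women may already have been enrolled without the item. For them, prespecify adjustment for education and earlier pelvic exam experience, and report that analysis as the weaker one.
5. Report the result as an association with mirror plus explanation, and say that residual confounding, such as motivation to learn, remains.

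The cost is one extra question on a form already in use and a few lines in Statistical Analysis. The design, sample size and visit flow are unchanged. The downside is a possible small testing effect, which may not be equal across cohorts.
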